5.8. Assessments

Refer to the Study Calendar in [Section 11.0](#).

6. ANTICIPATED TOXICITIES AND DOSE DELAY/MODIFICATION

6.1. Anticipated Toxicities

6.1.1. Ribociclib

A list of the adverse events and potential risks associated with ribociclib, as determined by the Package Insert follows (* signifies occurs in $\leq 10\%$):

Gastrointestinal: Nausea, stomatitis, diarrhea, decreased appetite, vomiting

General disorders and administration site conditions: Fatigue

Hematologic investigations: Abnormal absolute lymphocyte count; decreased lymphocytes, neutropenia, leukopenia, anemia, thrombocytopenia

Infections and infestations: Infection, upper respiratory tract infection*

Musculoskeletal and connective tissue: Weakness

Nervous system: Peripheral neuropathy

Respiratory, thoracic and mediastinal: Epistaxis

Skin and subcutaneous tissue: Alopecia

Vascular: Pulmonary embolism *

6.1.2. Letrozole

A list of the adverse events and potential risks associated with letrozole, as determined by the Package Insert follows (* signifies occurs in $> 10\%$; ** signifies occurs in $< 1\%$):

Cardiac: Myocardial infarction**, chest pain-cardiac**

Gastrointestinal: Nausea, vomiting, constipation*, diarrhea

General disorders and administration site conditions: Fatigue, edema*

Infections and infestations: Urinary tract infection

Injury, poisoning and procedural complications: Fracture

Investigations: Weight gain*, cholesterol high*, weight loss

Metabolism and nutrition: Anorexia

Musculoskeletal and connective tissue: Arthralgia*, myalgia, osteoporosis, weakness*, back pain, chest wall pain

Neoplasms benign, malignant and unspecified (including cysts and polyps): Treatment related secondary malignancy

Nervous system: Headache*, dizziness*, transient ischemic attack**

Psychiatric: Insomnia

Reproductive system and breast: Night sweats*, vaginal hemorrhage, vaginal irritation/ dryness, breast pain

Respiratory, thoracic and mediastinal: Dyspnea*, cough*

Vascular: Hot flashes*, thromboembolic event**

6.1.3. Exemestane

A list of the adverse events and potential risks associated with exemestane, as determined by the Package Insert follows (* signifies occurs in > 10%; ** signifies occurs in < 1%):

Cardiac: Myocardial infarction, angina, myocardial ischemia**

Eye: Visual disturbances

Gastrointestinal: Nausea*, diarrhea, constipation

General disorders and administration site conditions: Fatigue*, edema, increased sweating*, abdominal pain*

Immune system disorders: Allergy

Investigations: Weight gain*

Infections and infestations: Hepatitis

Injury, poisoning and procedural complications: Fractures

Metabolism and nutrition: Increased appetite, anorexia

Musculoskeletal and connective tissue: Arthralgia*, back pain, pain in limb, osteoarthritis, osteoporosis, myalgia

Nervous system: Headache*, dizziness, peripheral neuropathy**, paresthesia

Psychiatric: Insomnia*, depression*, anxiety*

Skin and subcutaneous tissue: Alopecia*

Vascular: Hot flashes*, hypertension*

6.1.4. Anastrozole

A list of the adverse events and potential risks associated with anastrozole, as determined by the Package Insert follows (* signifies occurs in > 10%):

Blood and lymphatic system: Anemia

Cardiac: chest pain-cardiac, myocardial ischemia

Eye: Cataract

Gastrointestinal: Nausea*, vomiting, dyspepsia

General disorders and administration site conditions: Edema limbs*

Infections and infestations: Pharyngitis*, infection, sinusitis, bronchitis, vaginal infection, urinary tract infection, hepatitis, rhinitis

Injury, poisoning and procedural complications: fractures*

Investigations: Weight gain, cholesterol high, Alkaline phosphatase increased, AST increased, ALT increased, bilirubin increased, GGT increased, hypercalcemia, lymphocyte count decreased, weight loss

Immune system disorders: Allergy, anaphylaxis

Musculoskeletal and connective tissue: Weakness*, arthritis*, arthralgia*, pain*, osteoporosis*, back pain*, bone pain*, arthrosis, myalgia

Neoplasms benign, malignant and unspecified (including cysts and polyps): Treatment related secondary malignancy, breast neoplasm

Nervous system: Headache*, dizziness, Ischemia cerebrovascular

Psychiatric: Depression*, insomnia*, anxiety, paresthesia

Reproductive system and breast: Vaginal discharge, breast pain, vaginal hemorrhage

Respiratory, thoracic and mediastinal: Cough*, dyspnea*

Skin and subcutaneous tissue: Rash*, Stevens-Johnson syndrome, erythema multiforme, urticaria, alopecia, pruritus

Vascular: Hot flashes*, hypertension*, lymphedema*, hypotension*, thromboembolic event

6.2. Dose Modifications/ Delays

6.2.1. General Information:

1. The cycle length will remain 28 days (\pm 2 days) despite a delay in initiating ribociclib on Day 1; endocrine therapy may continue to be administered per the preplanned schedule.
2. Dose holds/reductions of endocrine therapy will occur per treating investigator's discretion.
3. See [Table 6.2.1](#) for criteria to dose modify ribociclib. Dose reductions are as follows:

Table 6.2.1: Ribociclib dose levels

Dose Level	Dose
Starting dose	600 mg/day
First dose reduction	400 mg/day
Second dose reduction	200 mg/day
Third dose reduction	discontinue protocol therapy

Table 6.2.2a: Ribociclib Dose Modification and Management - Hematologic Toxicities

CTCAE v 4.0 Grade	Ribociclib Dose Modifications For Hematologic Toxicities
Grade ≤ 2	Maintain treatment.
Grade 3 (Except febrile neutropenia OR lymphopenia associated with clinical events)	Hold ribociclib until recovery to Grade ≤2. Consider repeating complete blood count monitoring one week later. 
 • Upon recovery Grade ≤2 within 28 days resume therapy at the pre-hold dose. • Permanently discontinue protocol therapy if the toxicity persists for > 28 days.
Grade 3 ANC (<1000 to 500/mm³) + Fever (≥38.5°C) OR Grade 3 ANC + infection	Hold ribociclib until recovery to Grade ≤2 ($\geq 1000/\text{mm}^3$). 
 • Upon recovery Grade ≤2 within 28 days resume therapy at the next lower dose. • Permanently discontinue protocol therapy if the toxicity persists for > 28 days.
Grade 4 ANC <500/mm³ (Except lymphopenia associated with clinical events)	Hold ribociclib until recovery to Grade ≤2. 
 • Upon recovery Grade ≤2 within 28 days resume therapy at the next lower dose. • Permanently discontinue protocol therapy if the toxicity persists for > 28 days.

Table 6.2.2b: Ribociclib Dose Modification and Management- Non-Hematologic Toxicities

	CTCAE v 4.0 Grade	Dose Modifications For Non-Hematologic Toxicities
RELATED to Ribociclib	Grade ≤ 2	Maintain treatment.
	Grade ≥ 3	
Hold ribociclib until recovery to Grade ≤1 or baseline.
 
 Upon recovery to Grade ≤1 or baseline within 28 days resume therapy at the next lower dose if medically appropriate at the discretion of the treating physician. Permanently discontinue protocol therapy if the toxicity persists for > 28 days
NOT-RELATED to Ribociclib	Grade ≥ 3	
Treating investigator may hold ribociclib per his/her discretion.
 
Permanently discontinue protocol therapy if the hold is for > 28 days

Table 6.2.2c: Ribociclib Dose Modification and Management- Hepatobiliary Toxicity

	Grade 1 (> ULN-3 x ULN)	Grade 2 (>3-5 x ULN)	Grade 3 (>5-20 x ULN)	Grade 4 (>20 x ULN)
AST and/or ALT Elevations from baseline, WITHOUT increase in total bilirubin above 2 x ULN	No dose adjustment required	
Baseline at < grade 2: Dose interruption until recovery to ≤ baseline grade, then resume ribociclib at the same dose level. If grade 2 recurs, resume ribociclib at the next dose level.
 
Baseline at grade 2:
 
No dose interruption
	
Dose interruption until recovery to ≤ baseline grade then resume at the next lower dose level. If grade 3 recurs, discontinue ribociclib.
	Discontinue ribociclib
Combined elevations in AST and/or ALT WITH total bilirubin increase, in the absence of cholestasis	If patient develops ALT and/or AST >3 x ULN along with total bilirubin >2 x ULN irrespective of baseline grade, discontinue ribociclib			

Table 6.2.2d: Ribociclib Dose Modification and Management- QT Prolongation

Grade	Dose Modification
For All Grades	
 1. Check the quality of the ECG and the QT value and repeat if needed. 2. Perform analysis of serum electrolytes (K+, Ca++, Phos, Mg++). If outside of the normal range, interrupt ribociclib administration, correct with supplements or appropriate therapy as soon as possible, and repeat electrolytes until documented as normal. 3. Review concomitant medication usage for the potential to inhibit CYP3A4 and/or to prolong the QT interval. 4. Check compliance with correct dose and administration of ribociclib. 
Consider collecting a time matched PK sample; record date and time of last study drug intake

1* QTcF 450-480 ms	Perform steps 1-4 as directed in “For All Grades.” No dose adjustment required.
2* QTcF 481-500 ms	
Interrupt ribociclib. Perform steps 1-4 as directed in “For all Grades.”
 
Perform a repeated ECG within one hour of the first QTcF of ≥ 481 ms.
 
Repeat ECG as clinically indicated until the QTcF returns to < 481 ms, restart ribociclib with dose reduced by 1 dose level. Refer to Table 6.2.1. for dosing schedule.
 
If QTcF ≥ 481 ms recurs, ribociclib should be reduced again by 1 dose level.
 
Repeat ECGs 7 days and 14 days after dose resumption (then as clinically indicated) for any patients who had therapy interrupted due to QTcF ≥ 481 ms.

3* QTcF ≥ 501 ms on at least two separate ECGs	
Interrupt ribociclib. Perform steps 1-4 as directed in “For All Grades.”
 
Perform a repeat ECG within one hour of the first QTcF of ≥ 501 ms.
 
If QTcF remains ≥ 501 ms, consult with a cardiologist (or qualified specialist) and repeat cardiac monitoring as indicated until the QTcF returns to < 481 ms.
 
 • If QTcF returns to < 481 ms, ribociclib will be reduced by 1 dose level. (Refer to Table 6.2.1 for dosing schedule.) • If QTcF returns to ≥ 481 ms after performing steps 1-4 as directed in “For All Grades,” discontinue ribociclib. 
Repeat ECGs 7 days and 14 days after dose resumption (then as clinically indicated) for any patients who had therapy interrupted due to QTcF ≥ 501 ms.
 
If QTcF of ≥ 501 recurs, discontinue ribociclib.

4* [QT/QTcF ≥ 501 or > 60 ms change from baseline] and [Torsades de pointes or polymorphic ventricular tachycardia, or signs/symptoms of serious arrhythmia]	
Discontinue ribociclib. Perform steps 1-4 as directed in “For All Grades.”
 
 • Obtain local cardiologist (or qualified specialist) consultation and repeat cardiac monitoring as indicated until the QTcF returns to < 481 ms.

*All values refer to the average of the triplicate measurements.

Dose Modification for Use with Strong CYP3A Inhibitors:

- Avoid concomitant use of ribociclib with strong CYP3A inhibitors and consider an alternative concomitant medication with less potential for CYP3A inhibition,
- If a strong CYP3A inhibitor must be coadministered, reduce the ribociclib dose to 400 mg once daily.
- If strong inhibitor is discontinued, change the ribociclib dose (after at least 5 half-lives of the strong CYP3A inhibitor) to the dose used prior to the initiation of the strong CYP3A inhibitor.

Dose Modification for Hepatic Impairment

- No dose adjustment is necessary in patients with mild hepatic impairment (Child-Pugh class A).

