The relationship between plasma trough and percent drop in neutrophil and platelet counts will be analyzed using linear models methods.

Abbreviated Eligibility Criteria:

Inclusion Criteria

- Hormone receptor positive metastatic breast cancer.
- First or second line endocrine therapy for metastatic disease. One prior line of chemotherapy for metastatic disease is allowed.
- Age: ≥ 70 years and life expectancy > 6 months
- Measurable disease per RECIST (1.1), or bone-only lytic or mixed lytic and blastic lesions that would be accurately assessed by means of computed tomography (CT) or magnetic resonance imaging (MRI).
- The ability to swallow and retain oral medication
- Resolution of all acute toxic effects of prior therapy or surgical procedures to CTCAE Grade ≤ 1 (except alopecia)

Exclusion Criteria

- Untreated brain metastases or symptomatic visceral spread at risk for life-threatening complications
- Concomitant CYP3A strong inhibitors or inducers
- Prior therapy with a CDK inhibitor

Investigational Product Dosage and Administration:

Ribociclib: Administered orally with food on Days 1-21 in each 28-day cycle. Starting dose: 600mg/day.
Aromatase inhibitor: Administered per treating investigator's discretion during each 28-day cycle; dosing should follow the package insert guidelines.

Clinical Observations and Tests to be Performed:

Clinical Observations/ Tests/ Questionnaires: medical history and demographics, physical exams, vital signs, performance status, routine laboratory tests, pill diary assessment, AE assessment, disease assessment, geriatric assessment, Was It Worth It Questionnaire assessment, Overall Treatment Utility assessment. Participants will be followed for survival.

Correlative Biology Studies: From participants who consent to research blood sample collection, a baseline sample of blood will be collected for future studies.

TABLE OF CONTENTS

SECTION	PAGE
Experimental Design Schema	3
Protocol Synopsis.....	4
Table of Contents	8
List of Tables and Figures.....	10
Abbreviations.....	11
1. Goals and Objectives (Scientific Aims).....	12
2. Background	12
2.1. Introduction/Rationale for Development	12
2.2. Rationale for Studying Cancer Therapy in Older Adults.....	12
2.3. Factors Other than Chronological Age that Impact Drug Tolerance	13
2.4. Ribociclib	14
2.5. Overview and Rationale of Study Design	15
3. Participant Eligibility Criteria	17
3.1. Inclusion Criteria	157
3.2. Exclusion Criteria.....	18

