7. Patient is currently receiving any of the following medications and cannot be discontinued 7 days prior to starting study drug (see Table 1 for details):
 - a. Known strong inducers or inhibitors of CYP3A4/5, including grapefruit, grapefruit hybrids, pummelos, star-fruit, and Seville oranges.

- b. That have a narrow therapeutic window and are predominantly metabolized through CYP3A4/5.
- c. Herbal preparations/medications, dietary supplements.
- d. Warfarin or other coumadin-derived anticoagulant for treatment, prophylaxis or otherwise. Therapy with heparin, low molecular weight heparin (LMWH), newer anti-coagulation agents such as direct factor Xa inhibitors, or fondaparinux is allowed

8. Patient is currently receiving or has received systemic corticosteroids \leq 2 weeks prior to starting study drug, or who have not fully recovered from side effects of such treatment.
 - a. The following uses of corticosteroids are permitted: single doses, topical applications (e.g., for rash), inhaled sprays (e.g., for obstructive airways diseases), eye drops or local injections (e.g., intra-articular).
9. Patient has impairment of gastrointestinal (GI) function or GI disease that may significantly alter the absorption of the study drugs (e.g., ulcerative diseases, uncontrolled nausea, vomiting, diarrhea, malabsorption syndrome, or small bowel resection).
10. Patient has any other concurrent severe and/or uncontrolled medical condition that would, in the investigator's judgment, cause unacceptable safety risks, contraindicate patient participation in the clinical study or compromise compliance with the protocol (e.g. chronic pancreatitis, chronic active hepatitis, active untreated or uncontrolled fungal, bacterial or viral infections, etc.).
11. Participation in a prior investigational study within 30 days prior to enrollment or within 5 half-lives of the investigational product, whichever is longer
12. Patient has had major surgery and/or radiotherapy within 14 days prior to receiving study drug or has not recovered from major side effects (tumor biopsy is not considered as major surgery).
13. Patient with a Child-Pugh score B or C.
14. Patient has not recovered from the acute effects of prior systemic therapy (until the toxicity resolves to either baseline or at least Grade 1) except for residual alopecia or peripheral neuropathy.
15. Patient has a history of non-compliance to medical regimen or inability to grant consent.

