5.7.1. Prohibited until end of protocol therapy

End of protocol therapy is when treatment with ribociclib will no longer continue.

- No other investigational therapy should be given to participants
- No anticancer agents other than the study medications administered as part of this study protocol should be given to participants. If such agents are required for a participant then the participant must first be withdrawn from the study.
- Co-medication that may interfere with study results; e.g. immuno-suppressive agents other than corticosteroids, such as systemic cyclosporine and tacrolimus are prohibited during the treatment phase of the study, unless discussed with principal investigator felt to be of low clinical risk to the participant.
- Use of herbal medications may have unknown interactions with the metabolism of the study agents, and therefore are prohibited from use during the treatment phase of the trial.
- Strong CYP3A inhibitors/inducers including St. John's Wort and Grapefruit. Refer to [Appendix B](#) for an extensive list.
- Drugs known to cause QT interval prolongation. Refer to [Appendix B](#) for an extensive list.
- Hormone replacement therapy, topical estrogens (including any intra-vaginal preparations), megestrol acetate and selective estrogen-receptor modulators (eg, raloxifene).

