APPENDIX B: PROHIBITED MEDICATIONS / MEDICATIONS TO BE USED WITH CAUTION

List of prohibited medications during study drug treatment

Category	Drug Name
Strong CYP3A4/5 inhibitors	Atazanavir/ritonavir, boceprevir, clarithromycin, cobicistat, conivaptan, danoprevir/ritonavir, darunavir/ritonavir, elvitegravir/ritonavir, grapefruit juice, idelalisib, indinavir, indinavir/ritonavir, itraconazole, ketoconazole, lopinavir/ritonavir, mibepradil, nefazodone, neflunavir, ombitasvir/paritaprevir/dasabuvir/ritonavir (VIEKIRA PAK), posaconazole, ritonavir, saquinavir/ritonavir, telaprevir, telithromycin, tipranavir/ritonavir, troleandomycin/voriconazole
Strong CYP3A4/5 inducers	carbamazepine ³ , enzalutamide, lumacaftor, mitotane, phenobarbital, phenytoin ³ , rifabutin, rifampin (rifampicin) ³ , St. John's wort (hypericum perforatum) ^{2,3}
CYP3A4/5 substrates with NTI¹	Alfentanil, astemizole, cisapride, cyclosporine, diergotamine (dihydroergotamine), ergotamine, fentanyl, pimozide, quinidine, sirolimus, tacrolimus
Medications with a known risk for QT prolongation⁴	Amiodarone, anagrelide, arsenic trioxide, astemizole, azithromycin, chloroquine, chlorpromazine, cilostazol, ciprofloxacin, cisapride, citalopram, clarithromycin, disopyramide, dofetilide, domperidone, donepezil, dronedarone, droperidol, erythromycin, escitalopram, flecainide, fluconazole, gatifloxacine, grepafloxacin, halofantrine, haloperidol, ibutilide, levofloxacin, levomepromazine, levosulpiride, methadone, moxifloxacin, ondansetron, oxaliplatin, papaverine HCl (intra-coronary), pentamidine, pimozide, procainamide, propofol, quinidine, roxithromycin, sevoflurane, sotalol, sulpiride, sultopride, terlipressin, terodilane, thioridazine, vandetanib
Herbal preparations/ medications	Herbal preparations/medications known as strong inducers or inhibitors of CYP3A4/5 or those with a known risk of QT prolongation are prohibited throughout the study. These herbal medications include, but are not limited to: St. John's wort, Kava, ephedra (ma huang), gingko biloba, dehydroepiandrosterone (DHEA), yohimbe, saw palmetto, and ginseng. Patients should stop using these herbal medications 7 days prior to first dose of study drug.

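### Section 6.2 sets a fixed ribociclib dose for use with strong CYP3A inhibitors, which Section 5.7.1 and Appendix B prohibit on treatment, and that dose does not fit Table 6.2.1 below the starting dose

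*Combined protocol and SAP*

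**What the plan says.** **During treatment.** Section 5.7.1 is headed "Prohibited until end of protocol therapy". One of its bullets begins "Strong CYP3A inhibitors/inducers including" and refers to Appendix B for the full list. In Appendix B, strong CYP3A4/5 inhibitors are the first category under "List of prohibited medications during study drug treatment".

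**Dose modification.** The block on strong CYP3A inhibitors at the end of Section 6.2 is softer. It starts with "Avoid concomitant use of ribociclib with strong CYP3A inhibitors", continues with "If a strong CYP3A inhibitor must be coadministered, reduce the ribociclib dose to 400 mg once daily", and adds that once the inhibitor has been stopped and washed out, ribociclib goes back "to the dose used prior to the initiation of the strong CYP3A inhibitor".

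**Dose levels.** Table 6.2.1 gives 600 mg/day at the start, 400 mg/day as the first reduction, 200 mg/day as the second, and discontinuation as the third.

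**Entry.** Exclusion 7a in Section 3.2 names "Known strong inducers or inhibitors of CYP3A4/5" among drugs that exclude a patient who cannot stop them 7 days before study drug. The synopsis lists "Concomitant CYP3A strong inhibitors or inducers" as an exclusion.

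**Analysis.** Sections 13.1.5 and 13.4 make dose reductions a secondary endpoint, reported as a rate with an exact 95% interval, and do not separate them by cause. The interim review in Section 13.3 turns on whether too many patients need a reduction. Section 10.5 averages each subject's troughs. Neither it nor Section 13.4 says how to treat a sample drawn on an inhibitor.

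**The concern.** The same act is provided for in Section 6.2 and is a departure from Section 5.7.1. Under Sections 7.2.1.1 and 7.2.2.1 a departure is a deviation to be notified within 5 calendar days. Sites reading different sections would manage, and report, the same patient differently.

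The safety stake comes from the protocol itself. Section 5.3.1 describes QT prolongation with ribociclib as concentration dependent, and Table 6.2.2d asks for a review of CYP3A4-inhibiting medication whenever the QT interval is prolonged.

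There is also a smaller statistical stake. Table 6.2.1 labels 400 mg/day as a dose reduction. A move to 400 mg/day because of an interaction would then look the same in the data as a move made for toxicity. The dose-reduction rate is read as a measure of tolerability and informs the interim decision on dose.

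**Working it through.** **1. The plan's own figures.** None is in dispute. With n = 40 and a true rate of 0.05, the chance of at least one event is 1 − 0.95^40 = 0.871, against 87 in 100 stated in Section 13.2. The exact interval for 20/40 is 0.338 to 0.662, half-width 0.162, against 0.34, 0.66 and 0.16 stated. Both reproduce to the precision given, and this point does not affect them.

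**2. Which passages conflict.**

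| Place | When it applies | Rule on strong CYP3A inhibitors |
|---|---|---|
| Section 3.2, exclusion 7a; synopsis | Entry | Excluded (in 7a, if the drug cannot be stopped 7 days before) |
| Section 5.7.1 | Until ribociclib ends | Prohibited |
| Appendix B | During study drug | Prohibited |
| Section 6.2 | During study drug | Avoid; fixed 400 mg/day if unavoidable |

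The conflict is between the last row and the two rows above it. The entry rules cover a different time and can stand beside a contingency for an inhibitor needed later.

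**3. The fixed dose against Table 6.2.1.** Change = 400 − current dose, also given as a share of the current dose.

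| Current dose | Change to 400 mg/day | Relative change |
|---|---|---|
| 600 mg/day | −200 mg | −33% |
| 400 mg/day | 0 | 0% |
| 200 mg/day | +200 mg | +100% |

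The instruction works as a reduction at one of the three active levels. At 200 mg/day a reduction to 400 mg/day is impossible as worded. By contrast, the toxicity-driven reductions elsewhere in Section 6.2 are stated relative to the patient's current level.

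**4. Effect on the dose-reduction rate.** The patient who matters is one moved from 600 to 400 mg/day for an interaction who never has a toxicity-driven reduction.

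- Final analysis: 1/40 = 0.025, or 2.5 points per patient.
- Interim with 20 patients: 1/20 = 0.05, or 5 points per patient.

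A patient already at 400 or 200 mg/day through toxicity steps is already counted as reduced, so the clause adds 0 points.

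As an illustration, assume 16 of 40 patients have toxicity-driven reductions (an assumption, not a figure in the plan):

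| Interaction-only patients added | Rate | Exact 95% limits |
|---|---|---|
| 0 | 16/40 = 40.0% | 24.9% to 56.7% |
| 1 | 17/40 = 42.5% | 27.0% to 59.1% |
| 4 | 20/40 = 50.0% | 33.8% to 66.2% |

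**5. Effect on troughs.** Table 10.2 has six pre-dose samples from Cycle 1 Day 1 to Cycle 2 Day 15. The first precedes any ribociclib, which leaves five that can carry drug. With 28-day cycles the last falls on study day 28 + 15 = 43. Only an inhibitor taken by then can affect the average.

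**The case against.** The best defence is that Section 6.2 is a fallback: the prohibition is the rule, and the fixed dose covers the rare patient for whom no alternative exists. That is a plausible intention, but the text does not state it. Section 5.7.1 does write an exception where one was wanted: immunosuppressive co-medication may be allowed after discussion with the principal investigator. The strong-inhibitor bullet has no such words and no cross-reference to Section 6.2. A note below the Appendix B list uses softer language about avoiding, as far as possible, drugs that raise QT risk, including through interactions. It does not take strong inhibitors off the prohibited list.

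Other objections do stand, and they limit the point. Four stronger readings are tempting:

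- **That the entry criteria also contradict Section 6.2.** They do not; they govern eligibility and washout before study drug.
- **That the protocol directs a doubled dose at 200 mg/day.** The verb is to reduce. An increase follows only if 400 mg/day is applied literally as a target and the verb is ignored. The supportable statement is that the instruction is unworkable at that level.
- **That every patient caught by the mismatch shifts the rate by 2.5 points.** This fails for patients already reduced for toxicity, as step 4 shows.
- **That the trough endpoint is compromised.** Entry requires washout and Section 5.7.1 forbids the drugs, so a strong inhibitor would have to be newly started within about six weeks. The documents give no sign of how often that would happen.

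It is also fair to say that the objective in Section 1.2 is to describe dose reductions, so restricting the endpoint to toxicity-driven ones would replace it with another. Likewise, a trough raised by an inhibitor is still a valid exposure value for the planned analysis against neutrophil and platelet falls. Neither is a reason to discard data.

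**Conclusion.** The point holds as an internal inconsistency. Section 5.7.1 and Appendix B cannot both be followed alongside the contingency in Section 6.2, and the fixed dose in that contingency fits Table 6.2.1 only for a patient at 600 mg/day. Nothing elsewhere in the document resolves either mismatch.

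The consequence for the endpoints is conditional. It arises only if a strong inhibitor is actually given and, for the dose-reduction rate, only for patients with no toxicity-driven reduction. Under those conditions the shift per patient is the one derived in step 4. The total cannot be estimated, because the frequency of inhibitor use and the resulting change in ribociclib exposure are not given. The case for correcting the text rests mainly on consistent conduct and safety, and only secondarily on the estimates.

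**What to change.** 1. The sponsor's clinicians should reconcile Section 5.7.1, Appendix B and the strong-inhibitor block of Section 6.2, and reconcile that block with every level in Table 6.2.1. Which rule or dose should apply is theirs to decide. Exclusion 7 needs no change on this account.
2. If coadministration remains possible, Section 13.4 should report dose reductions overall and by reason (toxicity or drug interaction), and Section 13.3 should use the same split at the interim review.
3. Sections 10.5 and 13.4 should flag troughs drawn on a strong inhibitor through Cycle 2 Day 15, keep them in the main summary, and add a sensitivity analysis of the average trough without them.

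The cost is protocol wording and one reason code on the treatment form. Footnote q of Table 11.0 already has concomitant medications recorded from 30 days before the first dose to 30 days after the last, so affected patients and samples can be identified from data the trial will collect anyway. The sample size does not change.
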